#### 6.4.5.1 Serology testing

Serology testing for HIV antibody, Hepatitis B (HBV), and Hepatitis C (HCV) will be performed on all patients at screening only. If the test result for HIV antibody is positive, the patient will not be allowed to proceed in the study.

Note: Although the results of the HIV and hepatitis screens must be documented in the patient's file, these results will not be collected on the eCRF and will therefore not be recorded in the study database.

#### 51(76)

#### 6.4.6 Physical examination

As detailed in Table 3, a physical examination will be performed at both Visit 1 and 5 by a medically qualified person.

The following should be assessed: general appearance, skin, head and neck (including ears, eyes, nose and throat), lymph nodes, musculo-skeletal (including spine and extremities), cardiovascular, lungs and abdomen.

Height (enrolment only) will be measured in centimetres and weight (enrolment only) in kilograms. Measurements should be taken without shoes and using calibrated scales for all measurements. BMI will be calculated from the height and weight.

#### 6.4.7 Resting 12-lead ECG

At Visits 1, 3 and 5, a resting 12-lead ECG will be performed as detailed in Table 3. The ECG will be performed at site according to local procedure.

ECGs will be recorded in the supine position after the patient has rested for 10 minutes. Heart rate, QRS duration, PR, RR QT intervals will be recorded, and QTcF (Fridericia-corrected) will be derived subsequently Overall evaluation of the ECG (normal, abnormal or borderline) should be recorded along with a note of any abnormalities and whether or not they were clinically significant. The original ECG traces must be stored in the patient's record as source data.

#### 6.4.8 Vital signs

#### 6.4.8.1 Pulse and BP

Vital signs (pulse and BP) will be measured at Visits 1, 2, 3, 4 and 5 as detailed in Table 3. Supine BP and pulse rate will be measured using non invasive equipment after a 10-minute rest on a bed.

#### 6.4.8.2 Body temperature

Body temperature (oral) will be measured in degrees Celsius using an automated thermometer at Visits 1, 2, 2b, 3, 4 and 5 as detailed in Table 3.

#### 6.4.9 Other safety assessments

## 6.4.9.1 Sputum quantitative microbiological analysis

A sample of sputum will be frozen for transport to a central laboratory for quantitative microbiological analysis using PCR (Visits 1a, 1b, 2, 3a, 3b and 4). Details will be included in the laboratory manual (There will not be any local bacterial culture).

## 6.5 Patient reported outcomes (PRO)

The methods for collecting PRO data are outlined below.

## 6.5.1 Bronkotest© diary card

The Bronkotest© diary card is a paper based diary card which will be given to the patients on entry into the study at Visit 1. Study site staff should provide a clear overview and guidance for the satisfactory completion of the diary card. The diary card will be completed on a daily basis by the patients at home and they should be instructed to bring it into each clinic visit. As a minimum, at Visits 2, 3, 4 and 5, the site staff should photocopy the pages that have been completed since last visit, review the diary and feedback any issues with unsatisfactory or ambiguous completion. The Investigator should review the content of the diary card and ensure that any information regarding AEs and medications are subsequently reflected in the eCRF. Missing values should not be completed by study site staff at the visit.

#### **Diary Card**

The Bronkotest© diary card is used to collect the patients assessment of their condition is provided in Table 7.

Question	Answer	Databased?
Describe your breathing	
 
1 – Better than usual
 
2 – Normal/Usual
 
3 – Worse than usual
 
4 – Much worse than usual
 
	Yes
What colour is your sputum?	Choose a number from 0 to 8 from sputum colour chart attached to Bronkotest © diary card	Yes
The amount of sputum you produced	
 
0 - None
 
1 - Some (up to a teaspoonful)
 
2 - A little (tablespoonful)
 
3 - Moderate (egg-cupful or more)
 
4 - A lot (cupful or more)
 
	Yes
Type of sputum?	1 – Watery 2 – Sticky Liquid 3 – Semi-Solid 4 – Solid	Yes
How do you feel?	
 
1 – Better than usual
 
2 – Normal/Usual
 
3 – Worse than usual
 
4 – Much worse than usual
 
	Yes

# Table 7Bronkotest© Diary Card variables

Question	Answer	Databased?
How often do you cough?	0 – Rarely 1 – Occasionally 2 – Frequently 3 – Persistently	Yes
Do you have chest pain?	Tick for yes	Yes
Do you have cold or flu?	Tick for yes	Yes
How much of your reliever medication have you taken today? (Enter number of puffs of inhalers, number of times of nebuliser use or number of tablets)	Free text field for a number to be inserted	Yes
Have you taken antibiotics/ steroid tablets today?	Tick for yes	Yes
Score the symptoms you have felt last night	
 
0 - Slept well
 
1 - Woke once because of chest symptoms
 
2 - Woke twice because of chest symptoms
 
3 - Woke more than twice because of chest symptoms
 
4 - Unable to sleep because of symptoms
 
	Yes
Peak Flow (morning)	Record value from peak flow meter	Yes
Peak Flow (evening)	Record value from peak flow meter	Yes
Regular treatment	Drug name and strength; Dose	No
New medication	Date; Drug name and strength; Dose; Reason	No
New antibiotics	Date; Drug name and strength; Dose; Reason	No
Symptoms of cold/flu	Tick if symptom is present; Date symptom started; Date symptom resolved	No
Additional comments	Free text field	No

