#### 5.6.3 Disallowed medication

In addition, the following treatments are not allowed:

- Use of oral corticosteroids in the 30 days prior to Visit 2 and throughout the study (NB: use of inhaled corticosteroids is allowed)
- Use of non-prophylactic antibiotics, systemic or nebuliser, in the 4 weeks prior to Visit 2 and throughout the study (NB: prophylactic use is allowed)
- Treatment with immunomodulatory agents within 8 weeks prior to Visit 2 and throughout the study
- Herbal medications, including but not limited to St John's Wort and Echinacea within 3 weeks prior to Visit 2 and throughout the study.

Although it is not expected from both non-clinical and in vitro data that AZD5069 at the dose to be used in this study will have any significant drug interactions, the following medications will not be allowed throughout the dosing period (ie, Visits 2 to 4):

- CYP2B6 substrates, in the 4 weeks prior to Visit 2, such as but not limited to: bupropion, cyclophosphamide, efavirenz, ifosfamide, selegiline, alfentanil, nevirapine, propofol, tamoxifen, valproic acid, artemisinin, pethidine, modafinil, sertraline, thiotepa
- PgP substrates, in the 4 weeks prior to Visit 2, including but not limited to: quinidine, tacrolimus, ivermectin, colchicines, etoposide, doxorubicin, vinblastine, protease inhibitors, non-nucleoside reverse transcriptase inhibitors, cyclosporin, digoxin
- Warfarin in the 4 weeks prior to Visit 2 and until completion of the study follow-up visit (Visit 5).

Any other drugs including inhaled and oral respiratory drugs could be allowed provided their doses have been stable for at least 4 weeks before enrolment and the doses remain unchanged throughout the study. SABA and/or SAMA may be taken as needed for symptomatic control of breathlessness.

Other medication which is considered necessary for the patient's safety and well-being, may be given at the discretion of the investigator and should be recorded in the electronic case report form (eCRF).

Please refer to Section 5.1 for other restrictions during the study.

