## **11.3** Calculation or derivation of patient reported outcome variables

## 11.3.1 Bronkotest© diary card data

Bronkotest© data that are numeric will be summarised as the mean of each period: Baseline period (last 7 days prior to start of treatment), Day 1 to Day 7, Day 8 to Day 14, Day 15 to Day 21, Day 22 to Day 28, end of treatment period (last 7 days on treatment) and follow-up (first 5 days after end of treatment). The change from baseline to treatment will be used as the outcome variable.

For Bronkotest $^{\circ}$  data that has a yes/no response, the frequency of yes responses by each period will be displayed.

Note: Morning and evening PEF recordings will be calculated separately.

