## 12.2.2 Secondary outcome variables

The secondary outcome variables are:

• Change from baseline (geometric mean of the values at Visits 1a, 1b and 2) to treatment (geometric mean of the values at Visit 3a, 3b and 4) in percentage neutrophils.

Approved

Date

ELECTRONIC DOCUMENT.

AN

ĿЮ

PRINTED COPY

К

5 H

THIS

PLEASE CHECK ITS VALIDITY BEFORE USE

- Change from baseline (Visit 1a or Visit 1b) to end of treatment (Visit 4) in 24-hour sputum collection weight.
- Change from baseline (Visit 2) to treatment (Visit 4) in FEV1.
- Change from baseline (Visit 2) to treatment (Visit 4) in SVC.
- Change from baseline (Visit 2) to treatment (Visit 4) in FEF25-75.
- Change from baseline (Visit 2) to treatment (Visit 4) in FVC.
- Change from baseline period (mean of last 7 days prior to start of treatment) to treatment period (mean of the last 7 days on treatment) in symptom score diary card (Bronkotest©).
- Change from baseline (Visit 2) to treatment (Visit 4) in mean total score and domain scores from St George's Respiratory Questionnaire.
- Change from baseline to treatment in sputum inflammatory markers including, but not limited to (and subject to the availability of validated assays): TNF-α, IL-8, IL-6, IL-1β, RANTES, MCP-1, GRO-α.
- Change from baseline to treatment in blood inflammatory markers including, but not limited to (and subject to the availability of validated assays): neutrophil concentration, TNF-α, IL-8, high sensitivity CRP, Amyloid-A, IL-6, IL-1β, GRO-α.
- Pharmacokinetic parameters (AZD5069 concentration measured in plasma).

The secondary outcome variables from the Bronkotest© diary card (continuous variables only), St George's Respiratory Questionnaire, lung function, 24-hour sputum weight, sputum and blood collections will be compared between AZD5069 and placebo using an analysis of variance model with fixed factors treatment and country (or centre) and using baseline as a covariate. Two-sided 90% CIs will be constructed for the treatment difference and p values given. For variables with a skewed distribution, data may be log-transformed prior to analysis or a non-parametric test (Wilcoxon rank sum) used instead. In addition, the statistical analysis and summary will be produced for data derived from BDI/TDI. The further details will be provided in the SAP.

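### The diary stores daily reliever use as one number with no unit and 11.3.1 averages it, so the mean mixes puffs, nebuliser uses and tablets, and a change of device can reverse the sign of a patient's change

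*Protocol*

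**What the plan says.** Table 7 in Protocol section 6.5.1 lists the diary items. The reliever item instructs the patient: "Enter number of puffs of inhalers, number of times of nebuliser use or number of tablets". The answer is a "Free text field for a number to be inserted", and the item is marked as databased. The row has no entry for unit, device, drug or strength.

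Section 11.3.1 sets the derivation. Diary "data that are numeric will be summarised as the mean of each period", and then: "The change from baseline to treatment will be used as the outcome variable". The reliever item is not excepted.

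Section 12.2.2 compares the arms by ANOVA with baseline as covariate, 90% confidence intervals and p values. For the diary it limits this in a parenthesis, "diary card (continuous variables only", and does not list which items it means. The diary outcome in that section's list is described as a symptom score; reliever use is not named.

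Section 5.6.3 says "SABA and/or SAMA may be taken as needed for symptomatic control of breathlessness". It does not tie this to one device.

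**The concern.** A puff, a nebuliser session and a tablet are different quantities. If the database holds only the count, a treatment-group mean adds them together and the result cannot be expressed in any unit. The same is true of the baseline value, which would be the covariate if the item were analysed under 12.2.2.

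A patient who moves between devices is the worse case, because the count can fall while the amount of reliever rises. Reliever use bears on the secondary objective about signs and symptoms, so a reader of the study report would want to know at least the direction of any change.

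The analysis plan could not reliably repair this. It can choose a method, but it cannot supply a unit that was never stored with the daily number.

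**Working it through.** The plan gives no figure for reliever use, so there is nothing to reproduce. The check sets the provisions side by side and then applies the stated rule to assumed values.

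**Which items does the rule reach?** Table 7 marks 13 items as databased:
- 7 are ordered codes (breathing, sputum colour, amount, type, general feeling, cough, night symptoms).
- 3 are ticks (chest pain, cold or flu, antibiotics or steroid tablets).
- 3 are open numbers (reliever use, morning peak flow, evening peak flow).

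Reliever use is plainly numeric, so 11.3.1 applies to it. It is also one of only three open numbers, so it plausibly falls within the continuous items of 12.2.2. That second step is an inference.

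**Case 1: no change of device (assumed values).** Outcome = treatment mean minus baseline mean.
- Patient A, 16 to 8 puffs a day: 8 - 16 = -8.
- Patient B, 4 to 2 nebuliser uses a day: 2 - 4 = -2.

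Both have halved their use, but A counts four times as much as B in the arm mean (8 / 2 = 4).

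**Case 2: change of device (assumed values).** Baseline 8 puffs a day, end of treatment 2 nebuliser uses a day.
- As planned: 2 - 8 = -6, which reads as an improvement.
- In puff equivalents, with k puffs per nebuliser use: 2k - 8. The protocol does not give k, so a range is shown.

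| k (puffs per use) | 2k - 8 | Sign of -6 |
|---|---|---|
| 2 | -4 | right |
| 4 | 0 | no true change |
| 8 | +8 | wrong |
| 10 | +12 | wrong |

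The break-even is 2k = 8, so k = 4. The reverse switch, 2 uses to 8 puffs, scores +6 and is a true decrease whenever k is above 4.

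**Case 3: both devices in one week.** Three days of 8 puffs and four days of 2 uses average (24 + 8) / 7 = 4.57. At k = 8 the same week is (24 + 64) / 7 = 12.57 puff equivalents. Against a baseline of 8, the stored data show a fall and the converted data a rise.

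**Effect on an arm mean.** One patient scoring -6 moves it by -6 / 25 = -0.24 with the 25 patients per group of section 12.3, or by -6 / 30 = -0.20 with the 30 to be randomised per group.

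**Do the stated alternatives help?** Section 12.2.2 allows a log transformation or a Wilcoxon test for skewed variables. Neither restores the unit: a change of -6 still ranks as a larger fall than a change of -2.

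**The case against.** The strongest reply has four parts.

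- **Medication is recorded elsewhere.** The same card asks for regular and new medication with drug name, strength and dose, and with a date for new items. Section 6.5.1 has the investigator transfer this to the eCRF, and Table 3 records concomitant medication at Visits 1, 2, 2b, 3, 4 and 5. Staff also review the diary for ambiguous entries. A newly started nebuliser should therefore be dated. This stands, and it makes the repair feasible. It does not attach a unit to each daily number, and a patient who already holds both devices stays ambiguous.
- **Testing is not stated.** The protocol never calls reliever use continuous and leaves further detail to the analysis plan. This also stands. The averaging and the change from baseline, however, are fixed in 11.3.1.
- **Switching may be rare and need not favour the drug.** Inclusion criterion 6 requires a stable regimen, and 5.6.3 asks for unchanged doses of other respiratory drugs, although SABA and SAMA remain as needed. A switch on placebo works against AZD5069, and a switch from nebuliser to inhaler can score as worsening. A reader might infer a bias towards benefit. The documents do not support that, because nothing shows that switching differs by arm.
- **Non-primary testing is exploratory.** Section 12.2.2 says so.

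Two further extensions are tempting and do not hold. A reader might object to the tick item, "Have you taken antibiotics/ steroid tablets today", because 5.6.3 permits preventive antibiotics ("NB: prophylactic use is allowed"). But 11.3.1 only displays yes/no items by period, the 7-day baseline period shows the same stable users, and the card records new antibiotics separately with date and reason. A reader might also infer that unmeasured reliever use undermines FEV1. Section 6.3.3 has spirometry done before any bronchodilator, and 5.6.2 has SABA withheld for 6 hours and SAMA for 8 hours as far as possible.

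**Conclusion.** The point holds for one diary item. As written, the plan produces a reliever mean without a unit. It weights patients by their device even when nobody switches, and it can give the wrong sign for a patient who does.

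The size rests on assumed values. The -6 in the example is a true increase only if one nebuliser use equals more than 4 puffs, and the protocol gives neither a conversion nor a frequency of device changes. The direction of any effect on the treatment comparison is unknown. That the item would go into the ANOVA is plausible but not stated.

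Severity is minor. The item is secondary and exploratory, and neither the primary analysis nor the sample size depends on it.

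**What to change.** 1. In 6.5.1, add a database field for the unit or device (puffs, nebuliser uses, tablets) beside the reliever number. Complete it at diary review from the patient's recorded reliever. The printed card need not change. The rule that staff do not fill in missing diary values is respected, because no patient answer is supplied.
2. In 11.3.1 and 12.2.2, state that the reliever number is not averaged or compared across units.
3. In its place, summarise days per period with any reliever use for all patients, and number of puffs only in patients who use inhalers alone in both the baseline and the treatment period.

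The cost is one database field and a few sentences of revised text. Days with any use is a coarser measure than a count, and the puff summary rests on a subset of patients.

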# Table 7Bronkotest® Diary Card variables

## 54(76)

GEL Version ID: RITA.000-335-908.4.0 Approved by

Approved

Date Printed:

The majority of the data will be databased; however, medication, cold and flu symptoms and any additional comments will not be databased directly but will be transferred into the relevant eCRF modules by the Investigator.

## Administration of PRO questionnaires

The Bronkotest© diary card is paper based and answers should be completed daily, by hand, by the patient at home.

#### 6.5.2 St George's Respiratory Questionnaire

The St George's Respiratory Questionnaire (SGRQ-C) will be completed by patients at Visits 2 and 4 (as outlined in Table 3). The questionnaire takes approximately 10 minutes to answer the questions.

#### Questionnaire

The St George's Respiratory Questionnaire (SGRQ) has been developed to measure the impact of respiratory disease on health status. The SGRQ-C is a shorter version of the SGRQ specially adapted for COPD (Meguro et al 2007). The SGRQ-C contains 3 domains: Symptoms (distress due to respiratory symptoms), Activity (disturbance of physical activity) and Impacts (overall impact on daily life and well being). The UK English version is attached in Appendix E, and is the version translated into other local languages as required.

#### Administration of PRO questionnaires

The SGRQ-C is paper based and answers should be completed, by hand, by the patient at the relevant clinic visits (refer to Table 3).

The SGRQ-C will be administered according to the guidelines for standardised administration. To avoid biasing responses, patients will answer the questionnaire at the clinic visits before any other study-related procedures take place.

The questions should be completed in a quiet place without influence from study personnel or accompanying family/friends. The subject should be informed about the importance of their participation and given adequate time to complete all items. No stated or implied time limit for completing the questionnaire will be given. If the subject should request help or clarification of any question in the questionnaire, study personnel are to instruct the subject to reread the instructions and to give the best answer possible to each question. Study personnel will not provide the subject with an answer to any question. After the subject has completed the questionnaire, the investigator or designee will review the questionnaire for completeness only. If the questionnaire (or any portion of it) is inappropriately incomplete, the subject will be given the opportunity to complete any missing items.

55(76)

PLEASE CHECK ITS VALIDITY BEFORE USE

AN ELECTRONIC DOCUMENT.

A PRINTED COPY OF

5 H

THIS

## 6.6 Pharmacokinetics

## 6.6.1 Collection of samples

Blood samples (4 mL KEDTA) for determination of AZD5069 in plasma will be taken at the times presented in the study plan Table 3.

Samples will be collected, handled, labelled, stored and shipped as detailed in the laboratory manual. The date and time of collection will be recorded.

For blood volume see Section 7.1.

## 6.6.2 Determination of drug concentration

Samples for determination of AZD5069 in plasma will be analysed by the appointed bioanalytical laboratory on behalf of Clinical Pharmacology & DMPK, AstraZeneca, using a validated method of liquid chromatography and mass-spectrometry (LC-MS/MS) after protein precipitation. The lower limit of quantification (LLOQ) of AZD5069 in plasma is 1.00 nmol/L.

Full details of the analytical method used will be described in a separate bioanalytical report.

All samples still within the known stability of the analyte of interest (ie, AZD5069) at time of receipt by the bioanalytical laboratory will be analysed. Additional analyses may be conducted on the biological samples to further investigate the presence and/or identity of drug metabolites. Any results from such analyses will be reported separately from the CSR.

## 6.7 Pharmacodynamics

## 6.7.1 Sputum inflammatory markers

The spontaneous sputum sample produced by the patient at the timings reflected in Table 3 will be processed locally. Samples will be sent to the local sputum processing laboratory within 2 hours of collection for processing. Resulting aliquots of supernatant will then be sent to the appropriate analysis laboratory. The supernatant aliquots produced will be used for the measurement of several pharmacodynamic markers in the sputum. Subject to validated assays being available the markers will include, but not limited to, TNF- $\alpha$ , IL-8, IL-6, IL-1 $\beta$ , RANTES, MCP-1, GRO- $\alpha$ . Sputum cytospins will be used to determine the total and differential cell count.

A priority list will be provided to the analysis laboratories to clarify what to do in the event of there being insufficient sputum aliquots to perform all detailed analyses.

Full details of sample handling and shipping can be found in the laboratory manual.

## 6.7.2 Blood inflammatory markers

Blood samples will be taken for assessment of inflammatory markers in serum. Subject to validated assays being available the markers in serum will be Amyloid-A and high-sensitivity

## 56(76)

Clinical Study Protocol Drug Substance AZD5069 Study Code D3550C00014 Edition Number 2 Date

CRP (hsCRP) and those in plasma will include, but not limited to, TNF- $\alpha$ , IL-8, IL-6, IL-1 $\beta$  and GRO- $\alpha$ .

The neutrophil cell count will be taken from the haematology safety sample taken at the corresponding visit.

